## Visit 14 (day 91 +/-2):

- Physical Exam
- DLQI
- HISCR
- PGA
- Disease Activity Score
- Modified Sartorius

- HADS
- VAS for disease
- VAS for pain
- Vital signs (blood pressure, pulse, oxygen saturation, respiratory rate and body temperature)
- Adverse event monitoring
- Concomitant medications/treatments

## 5.2 STUDY CALENDAR

Visit	Screen	1	2	3	4	5	6	7	8	9	10	11	12	13	14
Study Day		0 ± 2	7 ± 2	14 ± 2	21 ± 2	28 ± 2	35 ± 2	42 ± 2	49 ± 2	56 ± 2	63 ± 2	70 ± 2	77 ± 2	84 ± 2	91 ± 2
Informed Consent	x														
Demographics	x														
Medical/ Surgical History	x														
Infectious Disease Panel+ (part of blood draw)	x														
Serum Pregnancy (part of blood draw)	x														
Height, Weight, Body Mass Index (BMI)	x														
Vital Signs △	x	x	x	x	x	x	x	x	x	x	x	x	x	x	x
Urine Pregnancy		x	x	x	x	x	x	x	x	x	x	x	x	x	x
PK & Biomarker Blood Draw		x		x		x				x					x
Bermekimab Injection♦		x	x	x	x	x	x	x	x	x	x	x	x	x	x
DLQI		x		x		x		x		x		x		x	x
HADS		x		x		x		x		x		x		x	x
Physical Exam	x	x		x		x		x		x		x		x	x
Lab Blood Draw a,b,c	x		x		x					x				x	
HiSCR		x		x		x		x		x		x		x	x
PGA		x		x		x		x		x		x		x	x
Disease Activity Score		x		x		x		x		x		x		x	x
Modified Sartorius		x		x		x		x		x		x		x	x
VAS for disease		x		x		x		x		x		x		x	x
VAS for pain		x		x		x		x		x		x		x	x
Adverse Events		x	x	x	x	x	x	x	x	x	x	x	x	x	x
Concomitant Medications*	x	x	x	x	x	x	x	x	x	x	x	x	x	x	x

aChemistry Panel including: Albumin, Alkaline Phosphatase, ALT, AST, GGT, Bicarbonate (CO2) Calcium, Chloride, Creatinine, Glucose, Potassium, Sodium, Total Bilirubin, Total Protein, Urea Nitrogen

bHematology Panel including: Complete whole blood (WBC, HgB, Platelet, differential)

c CRP (C-Reactive Protein) and ESR (Erythrocyte Sedimentation Rate)

+ HIV antibody, Hepatitis C antibody, Hepatitis B panel (HBsAg, anti-HBc, anti-HBs), and interferon gamma release assay (IGRA)

△ Vital signs include blood pressure, pulse, oxygen saturation, respiratory rate and body temperature

♦ Each bermekimab injection will be followed by 1 hour monitoring for injection site reaction and vital signs 1 hour post injection (70+- 10 minutes)

\* Concomitant medications within 30 days before screening until 7 days after the last administration of the study drug must be recorded for the purpose of drug-drug and drug-disease interaction evaluation and signal detection.

**BMI:** Body Mass Index [BMI= weight (kg)/height (m^2)]

**DQLI:** Dermatology Quality of Life Index

**HiSCR:** Hidradenitis Suppurativa Clinical Response Score

**PGA:** Physicians' Global Assessment

**VAS:** Visual Analogue Scale

**HADS:** Hospital Anxiety Depression Scale

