**Secondary Endpoints:**

- Hidradenitis Suppurativa Clinical Response (HiSCR) from baseline (visit 1) to visit 13.
- Assessment of Pharmacokinetics (PK)
- Change in patient reported outcomes from baseline (visit 1) to visit 13 (VAS for disease, VAS for pain, DLQI).
- Change in Physician's Global Assessment (PGA), Disease Activity Score, and modified Sartorius score from baseline (visit 1) to visit 13.
- Change in inflammatory lesion (abscesses and inflammatory nodules) count from baseline (visit 1) to visit 13.
- Change from baseline (visit 1) to visit 13 in Hospital Anxiety Depression Scale (HADS).

**Trial Design\*****A Phase II, Open Label Study of Bermekimab in Patients with Moderate to Severe Hidradenitis Suppurativa**

- Group A (n=10): patients that have failed anti-TNF therapy will receive a total of 13 X 400mg weekly subcutaneous injections of bermekimab.
- Group B (n=10): patients that have no prior treatment with biological agents that block TNF will receive a total of 13 X 400mg weekly subcutaneous injections of bermekimab.

\*Restricted medications may be administered once during the study to alleviate acute exacerbation for HS symptoms.

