## **3. STUDY DESIGN AND OBJECTIVES**

Phase 2, Open label, multicenter study of two dose cohorts of bermekimab in patients naïve to or having failed prior anti-TNF therapy with moderate to severe Hidradenitis Suppurativa. Bermekimab administered subcutaneously at a dose of 400 mg weekly (13 doses). Patients will be followed for 13 weeks to allow for assessment of safety and preliminary efficacy.

The study protocol will be approved by the Institutional Review Board (IRB) or the Ethics Committee (EC) of the participating study sites. Depending on the participating countries both local and central IRB/EC approvals will be granted. The study will be registered at [www.clinicaltrials.gov](http://www.clinicaltrials.gov) before the enrollment of the first patient. The trial will be conducted in compliance with the protocol, GCP, and all applicable regulatory requirements.

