## Visit 13 (day 84 +/-2):

- ***At least 45 minutes before injection:*** Remove syringe from refrigeration and lay flat; allow to warm to room temperature. Do not heat
- Pre Injection
  - Physical Exam
  - DLQI
  - Urine pregnancy
  - HISCR
  - PGA
  - Disease Activity Score
  - Modified Sartorius
  - HADS
  - VAS for disease
  - VAS for pain
  - Blood draw for chemistry, hematology, CRP, ESR and blood draw for PK and biomarker analysis
  - Vital signs (blood pressure, pulse, oxygen saturation, respiratory rate and body temperature)
- Bermekimab subcutaneous injection, in accordance with injection site determined by BMI at Screening
- 1 hour monitoring for injection reactions
- Vital signs (blood pressure, pulse, oxygen saturation, respiratory rate and body temperature) one hour post injection (70 +/- 10 minutes)
- Adverse event monitoring
- Concomitant medications/treatments

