### **5.5 PATIENT CROSSOVER RULES**

Patients enrolled in the 200mg dose study are eligible to receive 400mg bermekimab injections upon consent to this protocol. Upon consent, patients will begin 400mg bermekimab dosing at next Study Day Visit, following patient calendar so that total number of bermekimab injections, 200mg + 400mg, is equal to 13 at end of study.

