## 7. ASSESSMENT OF SAFETY

Safety will be assessed by monitoring adverse events, vital signs, physical examinations, and clinical laboratory measurements. All subjects will be included in the safety analysis. Adverse events will be monitored from visit 1 (post-injection) through visit 14. Any serious adverse events or grade 2 or greater probably or definitely related events will be followed up until resolution.

Study drug will be administered under close observation in a facility equipped to handle anaphylaxis. Subjects must be closely monitored until at least 1 hour following the administration of the antibody or 1 hour after their vital signs have stabilized.

Any AE (with the exception of worsening HS symptoms or injection site reactions) of grade 2 or higher must be reported to the sponsor within 24 hours of learning of the event. Any grade 3 or greater injection site reaction must be reported to the sponsor within 24 hours of learning of the event.

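### The study calendar schedules a 14th bermekimab injection at visit 14, against 13 doses everywhere else, and its PK and safety-lab rows also differ from the visit text

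*Combined protocol and SAP*

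**What the plan says.** Four places fix the number of doses at 13:

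- Synopsis, Trial Design: each group "will receive a total of 13 X 400mg weekly subcutaneous injections of bermekimab".
- Section 3: bermekimab is given "at a dose of 400 mg weekly (13 doses").
- Section 5.5: patients crossing over from 200 mg continue "so that total number of bermekimab injections, 200mg + 400mg, is equal to 13 at end of study".
- Section 5.1: an injection is listed at every visit from 1 to 13. The last is under "Visit 13 (day 84 +/-2"). The list under "Visit 14 (day 91 +/-2") has no syringe warming, injection, post-injection monitoring, blood draw or urine pregnancy test.

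The calendar in section 5.2 differs. Its row "Bermekimab Injection" carries a mark at each of visits 1 to 14.

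On safety follow-up, section 7 states: "Adverse events will be monitored from visit 1 (post-injection) through visit 14". It adds: "Any serious adverse events or grade 2 or greater probably or definitely related events will be followed up until resolution". Section 9.3 likewise closes the recording of events at visit 14, or seven days after the last dose for patients who leave early.

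On sampling, sections 6.1 and 8.2 put PK samples pre-dose at visits 1, 3, 5, 9 and 13, and 5.1 agrees. Section 5.1 puts the on-treatment chemistry, hematology, CRP and ESR draws at visits 3, 5, 9 and 13.

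**The concern.** A visit calendar is an operating instruction, and many sites work from it directly. This one contradicts the dosing plan. A coordinator who follows the table would give a 400 mg dose on the last day of the study. The calendar's own footnote would require about an hour of monitoring after it, but no later visit exists at which a new event would be asked about. Safety and tolerability is the primary endpoint, so this gap falls on the main result.

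The sampling differences matter less. A PK and anti-drug-antibody sample at visit 14 falls outside the endpoint period, which ends at visit 13. Labs at visits 2 and 4 would come a week earlier than the text intends, so results labelled as the first and second on-treatment labs could refer to different study days at different sites.

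**Working it through.** **Inputs.** Visit *k* falls on day 7(*k* − 1), with a window of ±2 days (sections 5.1 and 5.2). Dose count: 13 (synopsis, sections 3 and 5.5). Exposure formula: (last injection − first injection) + 7 days (section 10.5.5).

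**Step 1: the plan's own figure.** Injections at visits 1 to 13 in section 5.1 make 13 doses, the last on day 7 × 12 = 84. Exposure is (84 − 0) + 7 = 91 days = 13 weeks, which matches the 13-week treatment period in the synopsis. Total dose is 13 × 400 = 5,200 mg.

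**Step 2: the calendar as printed.** Marks at visits 1 to 14 make 14 doses, the last on day 7 × 13 = 91. Exposure is (91 − 0) + 7 = 98 days = 14 weeks. Total dose is 14 × 400 = 5,600 mg.

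**Step 3: adverse-event collection after the last dose.** It ends at visit 14 (day 91). Text: 91 − 84 = 7 days. Calendar: 91 − 91 = 0 days.

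**Step 4: all repeat-visit rows against section 5.1.** The calendar has 16 such rows. Twelve match the visit text exactly: vital signs, DLQI, HADS, physical exam, HiSCR, PGA, Disease Activity Score, modified Sartorius, both VAS rows, adverse events and concomitant medications. Four do not:

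| Row | Calendar | Text |
|---|---|---|
| Injection | 1–14 | 1–13 |
| Urine pregnancy | 1–14 | 1–13 |
| PK | 1, 3, 5, 9, 14 | 1, 3, 5, 9, 13 |
| Safety labs | Screen, 2, 4, 9, 13 | Screen, 3, 5, 9, 13 |

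**Step 5: can the visit windows reconcile them?**

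| Draw | Calendar window (days) | Text window (days) | Distance between windows |
|---|---|---|---|
| First on-treatment lab | 5–9 | 12–16 | 12 − 9 = 3 |
| Second on-treatment lab | 19–23 | 26–30 | 26 − 23 = 3 |
| Last PK sample | 89–93 | 82–86 | 89 − 86 = 3 |

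No pair overlaps, so a sample on schedule under one version is off schedule under the other.

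**Step 6: combined draws.** In the text, labs and PK are taken together at four on-treatment visits (3, 5, 9, 13). In the calendar they coincide only at visit 9.

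**Step 7: what the late PK sample would measure.** At visit 13 pre-dose it is a 7-day trough after 12 doses. At visit 14 it is still a 7-day trough, but after 13 doses.

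**The case against.** The strongest reply is that nobody could misread the intent. Every section except one table row says 13 doses, visit 14 lacks every dosing step, and the exposure formula returns exactly 13 weeks only with 13 doses. The calendar's footnote collects concomitant medications until 7 days after the last dose; with a final column at day 91, that fits a last dose on day 84. Harm requires a site to follow one cell against all of this. Even then, section 9.6 requires serious events to be reported within 24 hours of knowledge, with no visit-14 cutoff, and section 7 follows some events to resolution. All of this stands, and it limits the consequence. It does not remove the contradiction, and new non-serious events after a day-91 dose would still have no scheduled collection.

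The second reply concerns the PK and lab rows. These are the only sparse, irregular rows among the repeat-visit rows, each has the same number of marks as the text requires, and the displaced marks are each one column off. That pattern could come from converting the PDF table to text. The 12 matching rows argue against a general column shift but cannot exclude a misplaced mark in a sparse row. This part therefore needs a source check. It does not reach the injection row: moving marks between columns does not turn 13 into 14.

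Third, the effect on analysis is modest. PK is summarised descriptively, and section 10.5.2.2 does not explicitly call for by-visit laboratory tables. The mixing of study days would matter for labs only if such tables are produced.

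**Conclusion.** The concern holds and should be fixed. Confidence is high for the injection row: 14 marks against 13 planned doses, which for a site following the table means one extra 400 mg dose and 0 instead of 7 days of scheduled adverse-event collection after the last dose. Confidence is medium for the PK position (day 91 against day 84) and the lab positions (days 7 and 21 against days 14 and 28), which assume that the marks stand in the source PDF where they appear in the converted text. The urine pregnancy mismatch at visit 14 is minor. No sample-size figure, analysis set or endpoint definition is affected.

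**What to change.** In section 5.2:

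1. Delete the injection mark at visit 14.
2. After checking the source table, move the last PK mark from visit 14 to visit 13.
3. After the same check, move the lab marks from visits 2 and 4 to visits 3 and 5.

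Then make the visit-14 urine pregnancy test consistent. Adding it to the visit-14 list in section 5.1 is a reasonable choice, because it keeps a test after the last dose.

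The cost is three corrected calendar rows and one added line in section 5.1, with no change to design, sample size or analysis.

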### **5.3 DISCONTINUATION OF THERAPY**

If a patient is discontinued from study, the reason for discontinuation must be clearly documented in the source documentation and the EDC.

Study therapy MUST immediately be discontinued for any the following reasons:

- Withdrawal of informed consent (subject's decision to withdraw for any reason)
- Any clinical adverse event, laboratory abnormality, inter-current illness, or clinical progression of disease which, in the opinion of the Principal Investigator, indicates that continued participation in the study is not in the best interest of the subject
- Pregnancy
- Termination of the study by the sponsor
- Imprisonment or the compulsory detention for medical treatment.

### **5.4 TRIAL STOPPING RULES**

Enrollment of any further patients for the trial will be suspended for the following events:

- The death of a subject at any time during the trial that is deemed to be probably or definitely related to the administration of bermekimab.
- Any significant safety finding assessed as definitely related to bermekimab that in the opinion of an Investigator warrants stopping the trial for additional assessment of safety.
- The occurrence of 2 or more serious adverse events occurring in one patient that are probably or definitely related to the administration of bermekimab.

### **5.5 PATIENT CROSSOVER RULES**

Patients enrolled in the 200mg dose study are eligible to receive 400mg bermekimab injections upon consent to this protocol. Upon consent, patients will begin 400mg bermekimab dosing at next Study Day Visit, following patient calendar so that total number of bermekimab injections, 200mg + 400mg, is equal to 13 at end of study.

## 6. CORRELATIVE STUDIES

### 6.1 PHARMACOKINETICS (PK) SAMPLE COLLECTION

An enzyme-linked immunosorbent assay (ELISA) has been developed to specifically measure bermekimab levels in human plasma. Blood will be drawn into a single 6 ml collection tube at each PK collection time point (sample collection is pre-dose at visit 1, visit 3, visit 5, visit 9 and visit 13). These samples will be collected per the study lab manual and immediately shipped to the Sponsor for PK analysis. The PK samples will also be used to test for the presence of antibodies against bermekimab.

## 7. ASSESSMENT OF SAFETY

Safety will be assessed by monitoring adverse events, vital signs, physical examinations, and clinical laboratory measurements. All subjects will be included in the safety analysis. Adverse events will be monitored from visit 1 (post-injection) through visit 14. Any serious adverse events or grade 2 or greater probably or definitely related events will be followed up until resolution.

Study drug will be administered under close observation in a facility equipped to handle anaphylaxis. Subjects must be closely monitored until at least 1 hour following the administration of the antibody or 1 hour after their vital signs have stabilized.

Any AE (with the exception of worsening HS symptoms or injection site reactions) of grade 2 or higher must be reported to the sponsor within 24 hours of learning of the event. Any grade 3 or greater injection site reaction must be reported to the sponsor within 24 hours of learning of the event.

## 8. STUDY VARIABLES

### 8.1 Demographic and Disease Characteristics

Demographic characteristics will include standard demography (age, sex, race, height, weight, and BMI) medical history, medication history, and prior biologic use for each patient. Characteristics of the patients with hidradenitis suppurativa, including duration of disease, baseline disease severity scores (HiSCR, modified Sartorius score, and physician's global assessment), baseline inflammatory lesion counts (abscesses and inflammatory nodules), and baseline patient reported

outcomes (VAS for pain, VAS for disease severity, and DLQI), will be collected. Baseline is defined as the visit 1, pre-injection assessment.

## 8.2 Study Endpoints

The primary endpoint of this study is the safety and tolerability of bermekimab at 400 mg weekly subcutaneous dose.

The secondary endpoints include:

- Hidradenitis Suppurativa Clinical Response (HiSCR) score (baseline to visit 13). For this score patients are defined as achievers or non-achievers. The positive HiSCR score is defined as a  $\geq 50\%$  reduction in inflammatory lesion AN count (sum of abscesses and inflammatory nodules), and no increase in abscesses or draining fistulas in HS compared with the lesions counted on visit 1. The HiSCR score, including inflammatory lesion count, will be measured on visits 1, 3, 5, 7, 9, 11, 13 and 14.
- Pharmacokinetics (PK) (baseline to visit 13). An enzyme-linked immunosorbent assay (ELISA) has been developed to specifically measure bermekimab levels in human plasma. Blood will be drawn into a single 6 ml collection tube at each PK collection time point (sample collection is pre-dose at visit 1, visit 3, visit 5, visit 9 and visit 13). These samples will be collected per the study lab manual and immediately shipped to the Sponsor for PK analysis. The PK samples will also be used to test for the presence of antibodies against bermekimab.
- Physician's Global Assessment (PGA) (baseline to visit 13). This is defined as: a) clear when the total number of abscesses is 0, the total number of draining fistulas is 0, the total number of inflammatory nodules is 0 and the total number of non-inflammatory nodules is 0; b) minimal when the total number of abscesses is 0, the total number of draining fistulas is 0, the total number of inflammatory nodules is 0 and there is presence of non-inflammatory nodules; c) mild when the total number of abscesses is 0, the total number of draining fistulas is 0, and the total number of inflammatory nodules is 1-4, or when there is presence of one abscess or draining fistula and absence of any inflammatory nodules; d) moderate when the total number of abscesses is 0, the total number of draining fistulas is 0 and the total number of inflammatory nodules is at least 5; or when there is presence of one abscess or draining fistula and at least one inflammatory nodule; or when there are 2-5 abscesses or draining fistulas and fewer than 10 inflammatory nodules; e) severe when the total number of abscesses or draining fistulas is 2-5 and the total number of inflammatory nodules is at least 10; and f) very severe when there

are more than 5 abscesses or draining fistulas. The PGA will be measured on visits 1, 3, 5, 7, 9, 11, 13 and 14.

- Disease Activity Score (baseline to visit 13). This is defined as the sum of scores of all affected areas of each patient. Each area will be evaluated by the following formula: (multiplication of the two largest diameters in each affected area in mm) x (the degree of inflammation of each lesion). This score has been proposed by our study group. The Disease Activity Score will be measured on visits 1, 3, 5, 7, 9, 11, 13 and 14.
- The modified Sartorius score (baseline to visit 13). The Sartorius Scale is used to quantify the severity of HS. Points are awarded for 12 body areas (left and right axillae, left and right sub/inframammary areas, intermammary area, left and right buttocks, left and right inguino-crural folds, perianal area, perineal area, and other): points were awarded for nodules (2 points for each); abscesses (4 points); fistulas (4 points); scars (1 point); other findings (1 point); and longest distance between two lesions (2-6 points, 0 if no lesions); and if lesions are separated by normal skin (yes-0 points; no-6 points). The total Sartorius score is the sum of the 12 regional scores. The modified Sartorius score will be measured on visits 1, 3, 5, 7, 9, 11, 13 and 14.
- Change in AN count (baseline to visit 13). The sum of abscesses and inflammatory nodules for each patient will be measured on visits 1, 3, 5, 7, 9, 11, 13 and 14.
- Change in VAS for Disease Severity and Pain (baseline to visit 13). Patient reported visual analogue scales for pain and disease severity will be measured on visits 1, 3, 5, 7, 9, 11, 13 and 14.
- Change in Dermatology Life Quality Index (DLQI) (baseline to visit 13). This will be measured on visits 1, 3, 5, 7, 9, 11, 13 and 14.
- Change in Hospital Anxiety Depression Scale (HADS) (baseline to visit 13). This will be measured on visits 1, 3, 5, 7, 9, 11, 13 and 14.

Changes in secondary endpoints will be presented by individual cohort, as well as combined across both cohorts.

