## **2.8 PROHIBITED AND RESTRICTED THERAPIES**

Treatment with certain restricted concomitant medications is allowed once during study to treat acute HS exacerbation, including:

- Systemic therapies with known effectiveness in HS, including corticosteroids, retinoids, or anti-androgen (hormonal) therapies.
- Intralesional/topical steroids
- Laser/light therapies

The use of rescue medications for worsening HS is to be reported in the electronic data capture system. A second flare up of disease and subsequent use of a second rescue therapy for any patient will result in the patient being treated as a non-responder for the purposes of data analysis.

The following concomitant therapies are *prohibited* for the entire duration of the trial:

- Biologics that target IL-1 or TNF-alpha
- Live virus vaccines
- Investigational agents other than bermekimab

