## 4. ELIGIBILITY CRITERIA

### 4.1 INCLUSION CRITERIA

**No waivers/exemptions will be granted for protocol inclusion/exclusion criteria.**

Subjects are included in the study if they meet all of the following criteria:

- Written informed consent provided by the patient.
- Male or female, age  $\geq 18$  years.
- For group A, patients must have received and failed anti-TNF therapy. For group B, subjects must not have received any prior treatment with any anti-TNF therapy.
- Patients who have received 200mg dose of bermekimab in this study are eligible to begin receiving 400mg dose starting with the patient's next scheduled visit for the remainder of his/her treatment plan.
- Diagnosis of HS for at least 1 year prior to screening.
- HS affecting at least two distinct anatomic areas, one of which is Hurley II or III stage.
- A total body count of abscesses and inflammatory nodules (AN) of at least 3
- Full understanding of the procedures of the study protocol and willingness to comply with them.
- In case of female patients of childbearing potential, willingness to use one method of contraception of high efficacy during the entire study period. This method can be hormonal contraceptives or one of the following: condoms, diaphragm, or an intrauterine device. Women of non-childbearing potential include those considered to have a medical history that indicates that pregnancy is not a reasonable risk, including post-menopausal women and those with a history of hysterectomy.

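### The lesion-count endpoints have no rule for a lesion drained or excised on study, so its removal can be scored as improvement

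*Combined protocol and SAP*

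**What the plan says.** **Endpoints (8.2).** A HiSCR achiever has a 50% or greater "reduction in inflammatory lesion AN count (sum of abscesses and inflammatory nodules), and no increase in abscesses or draining fistulas" compared with visit 1. For AN change, "The sum of abscesses and inflammatory nodules for each patient will be measured on visits 1, 3, 5, 7, 9, 11, 13 and 14". PGA is built from current totals; for example, a patient is "clear when the total number of abscesses is 0, the total number of draining fistulas is 0" and both nodule totals are also zero. Modified Sartorius adds regional points, including 2 per nodule, 4 for abscesses, 4 for fistulas and 1 for scars.

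**Entry (4.1).** "A total body count of abscesses and inflammatory nodules (AN) of at least 3" is required.

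**Concomitant treatment (2.8).** "Treatment with certain restricted concomitant medications is allowed once during study to treat acute HS exacerbation, including" three items: systemic therapies with known effect in HS, intralesional or topical steroids, and "Laser/light therapies". The prohibited list covers biologics against IL-1 or TNF-alpha, live virus vaccines and other investigational agents. Incision, drainage and excision are on neither list. The one stated consequence for the analysis is that a second flare and "subsequent use of a second rescue therapy for any patient will result in the patient being treated as a non-responder".

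**Surgery (4.2).** Only major surgery in the 28 days before visit 1 is addressed, as an exclusion.

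**Analysis (10.5.3).** The HiSCR proportion with a 95% CI, and descriptive changes for the other scores, are given by group and pooled. No rule concerns lesions removed by a procedure.

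**The concern.** Each of these scores asks what is present on the day. None asks why a lesion is absent. A lesion removed physically therefore contributes zero, exactly as one that healed does. The study is open label with no control group, so no comparator shows how much of an apparent response came from procedures.

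Section 1.2 describes flares with swelling, rupture and purulent discharge, so a procedure on a lesion during 12 weeks is foreseeable. It also says the study is meant to lay the basis for later randomised trials, for which the HiSCR proportion is a natural planning figure. With 10 patients per group, the classification of one patient is visible in the result.

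**Working it through.** The plan states no figure on this point (the sample size in 10.2 is one of convenience), so there is nothing to reproduce. The check applies the plan's own definitions to example counts.

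**Step 1: does any section close the gap?**
- 2.8 does not name drainage or excision. The list opens with a word that may make it non-exhaustive, so a procedure for a flare could be read as rescue. Even then the first use has no consequence in the analysis. Non-responder status also has a clear meaning for HiSCR but not for AN change, PGA or Sartorius.
- 4.2 restricts surgery only before the study.
- 9.3 asks that the underlying event, not the procedure, be recorded as the adverse event.
- 5.1 collects concomitant medications/treatments at visits 1 to 14, which may capture a procedure, but nothing links it to a lesion or a count.
- 10.5.3 adds nothing.

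**Step 2: removals needed for the 50% criterion.** For baseline AN of B, the fall must be at least 0.5 × B, so the number of lesions is B/2 rounded up.

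| Baseline AN | Highest AN that qualifies | Lesions that must go |
|---|---|---|
| 3 | 1 | 2 |
| 4 | 2 | 2 |
| 5 | 2 | 3 |
| 6 | 3 | 3 |
| 9 | 4 | 5 |
| 10 | 5 | 5 |

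At AN 3 or 4, two removals are enough with no other change, provided abscesses and draining fistulas do not increase. At AN 3 with one lesion cleared otherwise, one removal makes an achiever.

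**Step 3: the abscess condition.** Baseline 1 abscess + 5 inflammatory nodules gives AN 6. At visit 13, 2 abscesses + 1 nodule gives AN 3. That is a 50% fall, but abscesses rose from 1 to 2, so HiSCR fails. If one abscess was drained beforehand and is absent, the count is 1 abscess + 1 nodule, AN 2, and the patient is an achiever if fistulas have not increased.

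**Step 4: PGA (no fistulas).**
- 1 abscess + 2 inflammatory nodules is moderate; without the abscess it is mild.
- 6 abscesses + 2 nodules is very severe; with 5 abscesses it is moderate, two categories lower.
- 4 abscesses falling to 3, with fewer than 10 nodules, stays moderate.

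**Step 5: Sartorius.** Removing an abscess that leaves a scar changes that region by −4 + 1 = −3 points, other items unchanged.

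**Step 6: effect on the response rate.** One patient is 1/10 = 10 points in a group and 1/20 = 5 points pooled. The documents give neither an expected rate nor a procedure rate, so the rows below assume an as-observed rate of 60% and reclassify 0, 1 or 2 patients. Intervals are exact (Clopper–Pearson); the plan does not name its CI method.

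| Reclassified | Group of 10 | Pooled 20 |
|---|---|---|
| 0 | 6/10 = 60% (26.2–87.8) | 12/20 = 60% (36.1–80.9) |
| 1 | 5/10 = 50% (18.7–81.3) | 11/20 = 55% (31.5–76.9) |
| 2 | 4/10 = 40% (12.2–73.8) | 10/20 = 50% (27.2–72.8) |

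**The case against.** The case against has several parts, and much of it limits the point.

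- *The lesion might have cleared anyway.* Section 1.2 puts a typical flare at 3–5 days, ending in rupture and discharge. A lesion drained at visit 11 (day 70) could be gone by visit 13 (day 84) without intervention. Flare duration is not lesion duration, but this stands: not every removal is a false response.
- *The direction is not fixed.* A reader might infer that the error always favours the drug. The documents do not support that. A drained lesion later counted as a draining fistula would fail HiSCR, scars add Sartorius points, and PGA often does not move. A reader might also infer that a procedure shows the lesion had not responded. No section says so, and the lesion may be new since visit 1.
- *The rescue rule may already apply.* On a broad reading of 2.8, procedures in two separate flares give non-responder status. That is partial cover only, because the first is uncounted.
- *A carry-forward count can over-correct.* Take 0 abscesses and 6 nodules at visit 1. One new abscess drained at week 2 and counted as present thereafter is an increase in abscesses, so HiSCR fails even if every nodule clears. This is harsher than 2.8, which is why the as-observed result must be shown too.
- *The stakes are modest.* Safety is primary, HiSCR is one of several secondary endpoints and is never called the lead one, and its analysis is descriptive. Section 10 is only the basis for a revisable SAP, so a sensitivity analysis could still be added.

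What remains is that no section says how to count such a lesion, and the definitions as written can credit its removal as improvement.

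**Conclusion.** The gap is real and worth closing. HiSCR, AN count, PGA and modified Sartorius can all improve when a lesion is incised, drained or excised between visit 1 and visit 13. The direction is usually, not always, in favour of bermekimab.

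The total effect cannot be computed without a procedure rate. What can be stated is the sensitivity: two removals meet the 50% criterion at baseline AN 3 or 4 (five are needed at AN 9 or 10), and each reclassified patient is worth 10 points in a group of 10. The 5/10 versus 6/10 comparison is an illustration, and its intervals overlap heavily.

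A reader might go further and infer that the plan declares removed lesions to be resolved by the drug. It does not; it is silent, and the effect follows from day-of-visit counting combined with that silence. The conclusion assumes that such procedures occur on study and that assessors count only what they see.

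**What to change.** In 8.2 and 10.5.3:

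1. Define a lesion-directed procedure as incision, drainage, excision or similar physical removal. State whether intralesional steroid and laser fall under this counting rule or under the rescue rule in 2.8.
2. Count each lesion so treated after visit 1 once, in its pre-procedure class, as still present at later visits through visit 13. Apply this to HiSCR, AN change, PGA and the lesion points of the Sartorius score. Do not count a recurrence at the same site a second time.
3. Report the as-observed result beside it as a sensitivity analysis.
4. Record procedure date and lesion site under the existing concomitant medications/treatments item in 5.1.

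**Cost.** One counting rule, two fields on an existing form and one extra set of descriptive summaries. Response rates may be slightly lower. The rule is conservative for lesions that would have cleared anyway and for a new abscess drained early; the as-observed analysis shows how much that matters. The rule governs counting only and leaves clinical management unchanged.
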